3.4 STATISTICAL ANALYSES

3.4.1 GENERAL APPROACH

As a guide, the following should be addressed, as appropriate:

- *For descriptive statistics, describe how categorical and continuous data will be presented (e.g., percentages, means with standard deviations, median, range).*
- *For qualitative research, describe how procedural and interpretive rigor will be monitored and maintained*
- *For inferential tests, indicate the p-value and confidence intervals for statistical significance (Type I error) and whether one or two-tailed*
- *Indicate whether covariates will be pre-specified in the sections below or later in a SAP*
- *State whether checks of assumptions (e.g., normality) underlying statistical procedures will be performed and whether any corrective procedures will be applied (e.g., transformation or nonparametric tests)*

[*<Insert text>*](#)

3.4.2 ANALYSIS OF THE PRIMARY ENDPOINT(S)

Descriptive statistics will be calculated for all primary outcomes, which will be assessed through the collection of weekly diagnostic testing surveillance data (provided by SDHSA) and serial cross-sectional parent surveys. The primary outcome, diagnostic testing before and after implementation of the SASEA program will be examined using a mixed effects logistic regression with fixed effects for Time, SASEA program, and the interaction of Time x SASEA program. The mixed effects model will include a random component for school-level intercepts (to account for students nested within schools) and district-level intercepts (to account for schools nested in districts). Potential confounders will be controlled for in the

model (e.g., baseline COVID-19 diagnostic testing and vaccination rates within communities encompassing schools, school size, race/ethnicity, % receiving free/reduced lunch).

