END-OF-STUDY DEFINITION

A participant is considered to have completed the study if she or he has completed the community survey.

STUDY POPULATION

INCLUSION CRITERIA

In order to be eligible to participate in this study, an individual must meet all of the following criteria:

1. Parent with children enrolled at any of the 50 schools across the San Diego County that participated in the study during the 2021-2022 school year.
2. School staff working at any of the 50 schools across the San Diego County that participated in the study during the 2021-2022 school year.
3. Provision of signed and dated informed consent form
4. Access to necessary resources for participating in a technology-based intervention (i.e., computer, smartphone, internet access)

EXCLUSION CRITERIA

An individual who meets any of the following criteria will be excluded from participation in this study:

1. Not affiliated with participating sites as parents or staff.
2. No access to necessary resources for participating in a technology-based intervention (i.e., computer, smartphone, internet access)

LIFESTYLE CONSIDERATIONS

N/A

SCREEN FAILURES

N/A

STRATEGIES FOR RECRUITMENT AND RETENTION

This study will consist of a 20-week randomized stepped wedge cluster trial. Parents will be invited to participate in a 5–10-minute self-administered survey conducted at 4-week intervals. Prospective parent participants will be identified using a sampling frame provided by schools, at the beginning of the school year, consisting of classroom, classroom size, and grade level. Between 40 participating schools clustered and 8 childcare sites within 4 district clusters (approximately 12 sites per district cluster) will be enrolled during the study; for a total of 48 sites and 4 district clusters. The average size of school and childcare sites is 500. From the sampling frame, three classrooms within each school will be randomly selected. Within the randomly selected classroom, teachers will distribute a survey invitation to all students. Average class size is 25 and we anticipate a 25% response rate per class, resulting in approximately 20 surveys per site or approximately 150 surveys per cluster. Random samples of classrooms will be selected every 2-weeks with replacement using a randomization schedule generated by the study.

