3.2 SAMPLE SIZE DETERMINATION

Power was computed for a randomized stepped wedge design with 48 schools, 4 clusters (12 schools per cluster), and 5 steps with 1 cluster per step (or 4-week interval) based on diagnostic testing uptake in response to a positive environmental signal (see 1, responsive testing). Power is based on the primary outcome, on-site COVID-19 diagnostic testing uptake in response to a positive environmental signal in schools (see section A.4.1 and C.5.2). Published studies on the uptake of COVID-19 diagnostic testing among school-aged children and their household members in the presence of environmental surveillance are non-existent. We relied on testing rates observed in San Diego County schools during the latter half of the 2020-2021 academic year. Assuming a baseline COVID-19 testing rate of 2%, intra-class correlation $ICC=0.10$, Type I error rate of 0.05, and an average of 500 staff/students per school, we will have more than 80% power to detect a minimal difference of 0.06% in weekly testing uptake (2.0% pre SASEA-SNAP vs. 2.6% post SASEA-SNAP). Using similar assumptions for the secondary outcome, COVID-19 diagnostic testing uptake within household members of students, we will have over 80% power to identify a minimal detectable difference of 2.8% in testing uptake with a serial cross-sectional sample of 2,880 parents (2.0% pre SASEA-SNAP vs. 4.8% post SASEA-SNAP). Power was calculated in STATA 16.1 using a method described by Hemming and Girling

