3.3 POPULATIONS FOR ANALYSES

A random cross-sectional sample of parents and caregivers will be selected to participate in a 5–10-minute self-administered survey conducted at 4-week intervals (see Table 3). Prospective parent participants will be identified using a sampling frame provided by schools, at the beginning of the school year, consisting of classroom, classroom size, and grade level. From the sampling frame, three classrooms within each school will be randomly selected. Within the randomly selected classroom, teachers will distribute a survey invitation to all students. Average class size is 25 and we anticipate a 15% response rate per class, resulting in approximately 12 surveys per school or approximately 144 surveys per cluster; equating to 2,880 parent surveys during the 20-week period. Random samples of classrooms will be selected every 4-weeks with replacement using a randomization schedule generated by the study biostatistician, [name]. To increase generalizability, we will randomly select serial cross-sectional samples with replacement since serial samples will allow for greater representation given the likelihood of student absences on the day of recruitment (e.g., potential for individual students to be absent and/or classrooms to be quarantined due to COVID-19 exposure).

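### The primary model and the power calculation assume constant within-school correlation and no classroom clustering: modest type I inflation for the survey endpoint, and on-site power that is sensitive to the assumption

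*Combined protocol and SAP*

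**What the plan says.** Section 3.4.2, and the matching paragraph under Administration and/or Dosing, specify a mixed effects logistic regression. The fixed effects are time, intervention and their interaction. On the random side, "The mixed effects model will include a random component for school-level intercepts (to account for students nested within schools"), and a district intercept is added. No school-by-period, district-by-period or classroom term appears, and no robust variance or sensitivity analysis. Section 3.4.1, where these could have been set out, is unfilled template text.

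Section 3.3 describes the survey sample: in each school "three classrooms within each school will be randomly selected", the draw is repeated every 4 weeks with replacement, and some classrooms are expected to be quarantined.

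Section 3.2 computes power for a stepped wedge "with 48 schools, 4 clusters (12 schools per cluster), and 5 steps with 1 cluster per step (or 4-week interval"), with baseline testing of 2%, a single ICC of 0.10, a "Type I error rate of 0.05, and an average of 500 staff/students per school". It mentions no decay of correlation over time and no classroom or district component. It claims more than 80% power for two comparisons: 2.0% vs 2.6% for on-site testing, which it calls primary, and 2.0% vs 4.8% for household testing from 2,880 parent surveys, which it calls secondary. The Protocol Summary and the Objectives and Endpoints table instead make survey-reported testing of children in the past 14 days the primary endpoint.

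**The concern.** A school intercept alone says that two respondents from one school are equally correlated whether surveyed in the same wave or months apart. The fixed time effects remove only changes shared by all schools. A local outbreak, a quarantined classroom or the particular three classrooms drawn that month affects one school in one wave. The planned model treats that shared variation as independent between respondents.

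In a stepped wedge the Hub effect rests partly on before-and-after contrasts within schools, so school-by-period variation feeds directly into its error. If it is ignored, confidence intervals are too narrow and the test exceeds its nominal 5%. The power calculation shares the assumption. Its detectable differences are optimistic, most of all where many people per school are averaged and little other error remains.

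**Working it through.** **Inputs from the documents.** 48 schools in 4 sequences of 12; 5 periods (section 3.2's 5 steps, read as periods); ICC 0.10; alpha 0.05, taken as two-sided because no sidedness is stated; about 12 surveys per school-period (3 × 25 × 0.15 = 11.25; 48 × 12 × 5 = 2,880); 500 per school for the on-site outcome, read as per period.

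**Assumptions.** The documents give neither the CAC (the correlation between two periods divided by that within a period) nor a classroom ICC. CAC is varied from 0.8 to 1, and a classroom ICC of 0.05 is tried.

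**Variance of the Hub effect** (linear approximation, single Hub effect, total variance 1). Let τ² = 0.10 × CAC and σ² = 0.90/m + 0.10 × (1 − CAC), with I = 48 schools and T = 5 periods. The standard stepped-wedge formula is

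Var = Iσ²(σ² + Tτ²) / [(IU − W)σ² + (U² + ITU − TW − IV)τ²].

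Here U = 12 × (4+3+2+1) = 120, W = 12² + 24² + 36² + 48² = 4,320 and V = 12 × (16+9+4+1) = 360. The two coefficients are 5,760 − 4,320 = 1,440 and 14,400 + 28,800 − 21,600 − 17,280 = 4,320.

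**Reproducing the plan (CAC = 1).**
- On-site, m = 500: σ² = 0.0018; Var = 48 × 0.0018 × 0.5018 / (2.592 + 432) = 0.0000998; SE 0.00999. The outcome SD is 0.140 from the baseline variance (0.02 × 0.98) or 0.150 from the average of the two binomial variances. Power = Φ(0.006/(SE × SD) − 1.96) = 98-99%, so the claim of more than 80% holds. With 100 per period it would be 44-49%, which does not reproduce the claim.
- Survey, m = 12: σ² = 0.075; Var = 48 × 0.075 × 0.575 / (108 + 432) = 0.003833; SE 0.0619. With SD 0.140 to 0.181, power for 2.0% vs 4.8% is 71-90%. With average variance it comes close to the stated figure using 5 sequences (79.5%) or a one-sided test (80.5%).

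Both claims are therefore consistent with a constant-ICC calculation.

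**Allowing CAC below 1.** Power uses the formula above. As an example, on-site at CAC 0.95: σ² = 0.0068, τ² = 0.095, Var = 48 × 0.0068 × 0.4818 / (9.792 + 410.4) = 0.000374, SE 0.0193.

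Type I error compares the planned model's variance, which puts all non-school variance in the independent residual, with the true (sandwich) variance of the same estimator: type I = 2Φ(−1.96/R), where R = true SE / model SE. In the same example the model variance is 0.0001003 and the true variance 0.0003761, so R = √3.75 = 1.94 and type I error is 31%. For the survey at CAC 0.8 they are 0.003847 and 0.004692, so R = 1.10 and type I error is 7.6%.

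| Outcome | CAC | R | Type I error, planned model | Power |
|---|---|---|---|---|
| Survey, 12 per school-period | 1 | 1.00 | 5.0% | 71-90% |
| | 0.95 | 1.03 | 5.7% | 68-88% |
| | 0.90 | 1.05 | 6.3% | 66-86% |
| | 0.80 | 1.10 | 7.6% | 62-83% |
| On-site, 500 per school-period | 1 | 1.00 | 5.0% | 98-99% |
| | 0.98 | – | – | 79-84% |
| | 0.95 | 1.94 | 31% | 54-60% |
| | 0.90 | 2.54 | 44% | 35-39% |

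**Classroom clustering (survey only).** About 4 respondents share a classroom, so the design effect on the residual is 1 + 3 × 0.05 = 1.15. With CAC 0.8 this gives R of about 1.16 and type I error of about 9%.

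**Protocol Summary figures.** 971 surveys in 26 schools over an assumed 7 waves is 971/182 = 5.3 per school-wave. Type I error is about 5.2-6.0% over CAC 0.95 to 0.8.

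**Detectable difference, on-site, 80% power** (2.80 × SE × SD): 0.39-0.42 points at CAC 1, 0.57-0.61 at 0.98 and 0.76-0.81 at 0.95.

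**The case against.** The strongest reply is that the endpoint the Protocol Summary and objectives table call primary is the survey, and there the effect is small: about one percentage point at the Protocol Summary's sample size. That stands.

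Several stronger readings are tempting, and the documents do not support them.
- A reader might infer that the primary test has a 31-44% error rate. Those figures belong to 500 people per school-period. Section 3.4.2 names "weekly diagnostic testing surveillance data (provided by SDHSA") only in its sentence on descriptive statistics, and does not clearly say that those data enter the model. Which outcome is primary is a separate conflict.
- A reader might infer that the on-site power claim needs perfectly stable school rates. It holds at about 80% down to a CAC near 0.98.
- A reader might add the classroom and on-site effects together. They concern different data sets.
- A reader might infer that section 3.2 already carries a district term. It states one ICC only.
- A reader might assume district-wide shocks inflate the error further. That depends on whole districts switching together. The recruitment section speaks of 48 sites "for a total of 48 sites and 4 district clusters", in its words, while Administration and/or Dosing has schools randomized into the 4 clusters.

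The calculation is also not the planned analysis. It omits the interaction, the district intercept, the covariates and the logistic link at a prevalence near 2%, so the error rates are indicative.

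Finally, extra variance components may be hard to estimate. At 2.0-4.8%, 971 surveys yield about 19-47 events across 26 × 7 = 182 school-wave cells. That stands too, and the fix needs a fallback.

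**Conclusion.** The omission is real and nothing else in the document repairs it. The direction is certain whenever school-by-period or classroom variance exceeds zero; the size rests on a CAC and a classroom ICC that the documents do not give. For the survey endpoint the consequence is modest over CAC 0.95 to 0.8, and approaches a 9% error rate only at the lower end with classroom clustering added. For the on-site outcome the stated power is fragile: a CAC slightly below 0.98 takes it under 80%, reading 500 as the number per school in each period. If the planned model were applied to those data, its nominal 5% test would not be credible. This should be changed, but it does not by itself invalidate the survey analysis.

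**What to change.** In section 3.4.2 and the matching paragraph under Administration and/or Dosing, add a school-by-period random intercept. It also absorbs most of the variation shared within classrooms, because the classrooms drawn in a wave belong to that school and period. State in advance that if this component cannot be estimated because events are sparse, school-level cluster-robust standard errors with a small-sample correction will be used.

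Add a classroom intercept only as a sensitivity analysis, and only if classroom is recorded with each response; it is in the sampling frame, but nothing says it is kept with the survey. Add a district-by-period sensitivity analysis only if whole districts switch together.

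In section 3.2, state the assumed CAC and restate power and detectable differences over a range such as 0.8 to 1.0, separately for the survey and on-site outcomes.

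The cost is a few lines of text and one variance component, using identifiers the design already has. Intervals will be somewhat wider, the stated detectable difference less favourable, and convergence problems are possible.

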3.4.3 SAFETY ANALYSES

N/A

3.4.4 BASELINE DESCRIPTIVE STATISTICS

Include content in this section if applicable, otherwise note as “N/A.”

Intervention groups should be compared on baseline characteristics (e.g., demographics, laboratory measurements, behavioral characteristics) using descriptive statistics. Discuss planned baseline descriptive statistics, and indicate whether inferential statistics will be used.

<Insert text>

3.4.5 PLANNED INTERIM ANALYSES

N/A

3.4.6 SUB-GROUP ANALYSES

N/A

3.4.7 TABULATION OF INDIVIDUAL PARTICIPANT DATA

State whether individual participant data will be listed by measure and time point.

N/A

3.4.8 EXPLORATORY ANALYSES

All planned exploratory analyses should be specified in the protocol.

<Insert text>

4 SUPPORTING DOCUMENTATION AND OPERATIONAL CONSIDERATIONS

4.1 REGULATORY, ETHICAL, AND STUDY OVERSIGHT CONSIDERATIONS

4.1.1 INFORMED CONSENT PROCESS

4.1.1.1 CONSENT/ASSENT AND OTHER INFORMATIONAL DOCUMENTS PROVIDED TO PARTICIPANTS

Any consent forms will be approved by the IRB prior to research activity onset. Consent forms describing in detail the study intervention, study procedures, and risks will be given to the participant and written documentation of informed consent will be completed prior to starting the study intervention. The following consent materials are submitted with this protocol: consent form for community survey.

4.1.1.2 CONSENT PROCEDURES AND DOCUMENTATION

Consent forms will be required to be completed prior to starting the community survey. Consent forms will be available in English and Spanish. An email address and phone number will be provided if individuals have questions.

STUDY DISCONTINUATION AND CLOSURE

This study may be temporarily suspended or prematurely terminated if there is sufficient reasonable cause. Written notification, documenting the reason for study suspension or termination, will be provided by the suspending or terminating party to study participants, investigator, funding agency, and regulatory authorities. If the study is prematurely terminated or suspended, the Principal Investigator (PI) will promptly inform study participants, the Institutional Review Board (IRB), and sponsor/funding agency and will provide the reason(s) for the termination or suspension. Study participants will be contacted, as applicable, and be informed of changes to study visit schedule.

Circumstances that may warrant termination or suspension include, but are not limited to:

- Determination of unexpected, significant, or unacceptable risk to participants
- Demonstration of efficacy that would warrant stopping
- Insufficient compliance of study staff to the protocol (ie, significant protocol violations)
- Data that are not sufficiently complete and/or evaluable
- Determination that the primary endpoint has been met
- Determination of futility

The study may resume once concerns about safety, protocol compliance, and data quality are addressed, and satisfy the funding agency and IRB

4.1.2 CONFIDENTIALITY AND PRIVACY

Participant confidentiality and privacy is strictly held in trust by the participating investigators, their staff, the safety and oversight monitor(s), and the sponsor(s) and funding agency. This confidentiality is extended to the data being collected as part of this study. Data that could be used to identify a specific study participant will be held in strict confidence within the research team. No personally-identifiable information from the study will be released to any unauthorized third party without prior written approval of the sponsor/funding agency.

All research activities will be conducted in as private a setting as possible.

There will be no medical records collected for this study.

The study participant's contact information will be securely stored at each clinical site for internal use during the study. At the end of the study, all records will continue to be kept in a secure location for as long a period as dictated by the reviewing IRB, Institutional policies, or sponsor/funding agency requirements.

Study participant research data, which is for purposes of statistical analysis and scientific reporting, will be transmitted to and stored on a secure server at UCSD. This will not include the participant's contact or identifying information. Rather, individual participants and their research data will be identified by a unique study identification number. The study data entry and study management systems used by UCSD research staff will be secured and password protected. At the end of the study, all study databases will be de-identified and archived at Redcap.

Measures Taken to Ensure Confidentiality of Data Shared per the NIH Data Sharing Policies

It is NIH policy that the results and accomplishments of the activities that it funds should be made available to the public (see <https://grants.nih.gov/policy/sharing.htm>). The PI will ensure all mechanisms used to share data will include proper plans and safeguards for the protection of privacy, confidentiality, and security for data dissemination and reuse (e.g., all data will be thoroughly de-identified and will not be traceable to a specific study participant). Plans for archiving and long-term preservation of the data will be implemented, as appropriate.

Certificate of Confidentiality

To further protect the privacy of study participants, the Secretary, Health and Human Services (HHS), has issued a Certificate of Confidentiality (CoC) to all researchers engaged in biomedical, behavioral, clinical or other human subjects research funded wholly or in part by the federal government. Recipients of NIH funding for human subjects research are required to protect identifiable research information from forced disclosure per the terms of the NIH Policy (see <https://humansubjects.nih.gov/coc/index>). As set forth in 45 CFR Part 75.303(a) and NIHGPS Chapter 8.3, recipients conducting NIH-supported research covered by this Policy are required to establish and maintain effective internal controls (e.g., policies and procedures) that provide reasonable assurance that the award is managed in compliance with Federal

statutes, regulations, and the terms and conditions of award. It is the NIH policy that investigators and others who have access to research records will not disclose identifying information except when the participant consents or in certain instances when federal, state, or local law or regulation requires disclosure. NIH expects investigators to inform research participants of the protections and the limits to protections provided by a Certificate issued by this Policy.]

Survey data will be securely stored in UCSD's REDCap database. Study personnel accessing the data will be required to access UCSD's VPN and Active Directory log in to enter REDCap. We take care to ensure that participants cannot be identified on the basis of a combination of metadata values (e.g zip code). Qualitative data transcripts will be stored in UCSD's Microsoft One Drive.

4.1.3 FUTURE USE OF STORED SPECIMENS AND DATA

Survey data collected for this study will be analyzed and stored at Duke University using the RADxUp database. After the study is completed, the de-identified, archived data will be transmitted to and stored at the RADxUp database, for use by other researchers including those outside of the study. Permission to transmit data to the RADxUp database will be included in the informed consent.

When the study is completed, access to study data will be provided through the RADxUp database managed by Duke University. There will be no specimens collected for this study.

